#### STATEMENT OF COMPLIANCE

The trial will be carried out in accordance with International Conference on Harmonisation Good Clinical Practice (ICH GCP) and the following:

• United States (US) Code of Federal Regulations (CFR) applicable to clinical studies (45 CFR Part 46, 21 CFR Part 50, 21 CFR Part 56, 21 CFR Part 312, and/or 21 CFR Part 812)

National Institutes of Health (NIH)-funded investigators and clinical trial site staff who are responsible for the conduct, management, or oversight of NIH-funded clinical trials have completed Human Subjects Protection and ICH GCP Training.

The protocol, informed consent form(s), recruitment materials, and all participant materials will be submitted to the Institutional Review Board (IRB) for review and approval. Approval of both the protocol and the consent form must be obtained before any participant is enrolled. Any amendment to the protocol will require review and approval by the IRB before the changes are implemented to the study. In addition, all changes to the consent form will be IRB-approved; an IRB determination will be made regarding whether a new consent needs to be obtained from participants who provided consent, using a previously approved consent form.

## 1 PROTOCOL SUMMARY

## 1.1 SYNOPSIS

**Title:** A Phase 2 trial of the effect of tolebrutinib, a brain-penetrant Bruton's tyrosine kinase inhibitor, on chronically inflamed white matter lesions in multiple sclerosis

**Study Description:** The primary goal of this protocol is to test whether 48 weeks of treatment with tolebrutinib, an investigational, orally available, brain-penetrant, Bruton's tyrosine kinase (BTK) inhibitor, affects an imaging marker (the "paramagnetic rim") associated with chronically inflamed white matter lesions in multiple sclerosis (MS). In this rater-blinded but otherwise open-label study, 16 adults with MS who are on stable disease-modifying treatment with anti-CD20 antibody therapy and are within 6 months of their most recent dose, have at least one paramagnetic rim lesion on 7-tesla magnetic resonance imaging (MRI), and have developed no new white matter lesions or clinical relapses for at least 6 months, will initiate treatment with tolebrutinib and agree to forego further anti-CD20 or other disease-modifying therapy for the duration of the trial.

An initial 7 enrolled study participants started tolebrutinib at 60 mg/day ("Initial Cohort"). Of the Initial Cohort, participants (n=3), who had initiated tolebrutinib 60 mg will remain at 60 mg and not be escalated to 120 mg/day. The remaining participants (n=4) consented to Cohort A, who had initiated tolebrutinib 60 mg and previously escalated to 120 mg/day will remain at that dose.

Radiological, clinical, and biological outcomes are measured at 24, 48, 72, 96, and 144 (Cohort A) weeks, with additional interspersed visits for safety monitoring. Participants may subsequently continue treatment until tolebrutinib is marketed or commercial development halted. A comparison group of 10 participants who meet enrollment criteria but choose to stay on anti-CD20 therapy will also be enrolled. The primary outcome measure is disappearance of one or more paramagnetic rims from white matter lesions identified at baseline. Secondary outcomes include safety and tolerability and additional radiological outcomes. Exploratory clinical, radiological, and laboratory investigations are planned to study the mechanism of action of tolebrutinib and for biomarker development, and to compare the tolebrutinib and anti-CD20 cohorts.

**Objectives:** *Primary Objective:* To evaluate the effects of 48 weeks of tolebrutinib 60 mg/day treatment on the paramagnetic rim of chronically inflamed white matter lesions, as seen on 7-tesla MRI.

Secondary Objectives: (1) To assess safety and tolerability of 48 weeks of treatment with tolebrutinib 60 mg and 96 weeks of treatment with tolebrutinib 120 mg (Cohort A) all following anti-CD20 antibody therapy. (2) To assess the possible repair of chronically inflamed white matter lesions in which inflammation at the lesion edge has been modulated by tolebrutinib.

**Endpoints**: *Primary Endpoint*: Per-patient proportion of lesions in which the paramagnetic rim has disappeared at the end of 48 weeks of tolebrutinib 60 mg.

Secondary Endpoints: (1) Adverse event tables. (2) Changes in T1 relaxation time within paramagnetic rim lesions at the end of 96 weeks of tolebrutinib 120 mg, relative to non-rim lesions. (3) Changes in size of paramagnetic rim lesions at the end of 96 weeks of tolebrutinib 120 mg, relative to non-rim lesions.

**Study Population:** Up to 10 adults with multiple sclerosis, targeting at least 7 participants who complete 48 weeks of therapy with tolebrutinib 60 mg in Cohort A. Up to 10 adults with multiple sclerosis who meet inclusion criteria but choose to stay on anti-CD20 therapy.

Phase: 2

[figure not shown]
**Description of Study Intervention:** Oral tolebrutinib 60 mg per day for 48 weeks (Initial Cohort), and a subgroup of patients already escalated to 120 mg (Cohort A), with optional long-term extension and follow-up.

**Study Duration:** 5 years

[figure not shown]
**Participant Duration:** 144 weeks (Cohort A) for primary and secondary outcomes, with optional long-term extension and follow-up.

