# 6.1.2 Dosing and Administration

# 6.1.2.1 Dose Escalation

As of January 20, 2023, participants (n=4) who started tolebrutinib 60 mg/day and previously escalated to 120 mg/day† at Week 48 will remain at that dose. Participants (n=3) who initiated tolebrutinib 60 mg/day and did not escalate to 120 mg/day due to the partial clinical hold will be followed on study for an additional 48 weeks, according to the schedule of the Initial Cohort. They will furthermore be eligible to continue taking tolebrutinib 60 mg/day until tolebrutinib becomes FDA-approved or the clinical development program is terminated.

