# 6.1.2.5 Partial Clinical Hold

On June 29, 2022, we were informed by Sanofi that as of June 27, 2022, new enrollment was being halted across all 5 of their US phase 3 trials of tolebrutinib, and that all participants dosed after April 29, 2022 in the US would be required to stop tolebrutinib but would continue for observation on the trials. Sanofi staff detailed a call earlier in the week, on which the FDA verbally communicated a partial clinical hold to the Sponsor. The partial clinical hold was enacted after internal discussions regarding four participants with evidence of drug-induced liver injury (DILI), and the FDA outlined specific steps that Sanofi could take to support lifting the hold.

On July 12, 2022, the FDA issued a partial clinical hold to the NINDS IND as well, with identical stipulations to the Sanofi hold. As such, until the hold is lifted, we will not initiate new subjects on tolebrutinib. However, as no participants in our study had been taking tolebrutinib for less than 60 days at the time of

<sup>† See Section 6.1.2.5

the FDA partial clinical hold, the FDA does not require that we stop tolebrutinib for any participant in our trial. Furthermore, although not specifically stipulated by the FDA, we have elected to defer dose escalation from 60 to 120 mg (the "week 48" time point) until the partial clinical hold is lifted or modified; once the dose is escalated, however, the trial clock will restart.

On January 20, 2023, the FDA requested a revision to the protocol to remove the potential for dose escalation. Participants who have initiated tolebrutinib 60 mg and escalated to 120 mg/day will remain at that dose. The 3 remaining participants who initiated tolebrutinib 60 mg will remain at 60 mg and not be escalated to 120 mg/day.

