# 9.1 STATISTICAL HYPOTHESIS

- Primary Endpoint: The per-participant proportion of lesions in which the paramagnetic rim has disappeared at the end of 48 weeks of tolebrutinib 60 mg treatment is >0.01.
- Secondary Endpoints:
  - Tolebrutinib 60 and 120 mg doses are safe and tolerable in the study population.
  - The T1 relaxation time has decreased in paramagnetic rim lesions at the end of 96 weeks of tolebrutinib 120 mg, relative to non-rim lesions.
  - The size of paramagnetic rim lesions has diminished at the end of 96 weeks of tolebrutinib 120 mg, relative to non-rim lesions.

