# 9.4 STATISTICAL ANALYSES

9.4.1 General Approach

# 9.4.2 Analysis of the Primary Endpoint

The primary outcome is the per-patient proportion of lesions in which the paramagnetic rim has disappeared at the end of 48 weeks of tolebrutinib 60 mg/day, in comparison to the scan just prior to initiation of tolebrutinib dosing. Such participants can be in Cohort A or the Initial Cohort (combined analysis). Proportion of diminished/resolved paramagnetic rims is analyzed by investigators blinded to time point, reported descriptively, and compared to the assumption of no change off therapy via a binomial exact test. The analysis will be performed in study completers, and by definition no data will be missing. A threshold p-value of 0.05 will be taken as a significant change.

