# 9.4.3 Analysis of the Secondary Endpoints

To assess the possible repair of chronically inflamed white matter lesions in which inflammation at the lesion edge has been modulated by tolebrutinib 120 mg/day, changes in T1 relaxation time within paramagnetic rim lesions, relative to non-rim lesions, will be determined by analysis of variance or mixedeffects models. Comparisons are relative to the scan taken just prior to initiation of 120 mg dosing. A threshold p-value of 0.025 will be taken as a significant change.

To assess the possible repair of chronically inflamed white matter lesions in which inflammation at the lesion edge has been modulated by tolebrutinib 120 mg/day, changes in size of paramagnetic rim lesions, relative to non-rim lesions, will be determined by analysis of variance or mixed-effects models. Comparisons are relative to the scan taken just prior to initiation of 120 mg dosing. A threshold p-value of 0.025

will be taken as a significant change.

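### Holm's step-down rule for the two MRI repair endpoints would be a cheap gain over a fixed 0.025 each, at the same 5% bound; the present rule is valid

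*Combined protocol and SAP*

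**What the plan says.** The Synopsis (1.1) lists two MRI endpoints for repair: "Changes in T1 relaxation time within paramagnetic rim lesions at the end of 96 weeks of tolebrutinib 120 mg, relative to non-rim lesions" and "Changes in size of paramagnetic rim lesions at the end of 96 weeks of tolebrutinib 120 mg, relative to non-rim lesions". Section 9.1 states them as separate directional hypotheses: "The T1 relaxation time has decreased in paramagnetic rim lesions at the end of 96 weeks of tolebrutinib 120 mg, relative to non-rim lesions", and "The size of paramagnetic rim lesions has diminished at the end of 96 weeks of tolebrutinib 120 mg". In Section 3 both stand under one and the same repair objective.

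The Synopsis gives no threshold. Sections 3 and 9.4.3 do, once for each endpoint: "A threshold p-value of 0.025 will be taken as a significant change". Neither section sets an order, a step-down rule or any reuse of alpha. Neither explains the 0.025, names an overall level or says whether the tests are one- or two-sided. Analysis is by ANOVA or mixed-effects models in completers, against the scan before the 120 mg dose.

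The remaining secondary endpoint, adverse events, is only tabulated (9.4.4). The primary has its own criterion in 9.4.2: "A threshold p-value of 0.05 will be taken as a significant change". So exactly two tests carry the 0.025.

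On numbers, Section 6.1.2.1 refers to "participants (n=4) who started tolebrutinib 60 mg/day and previously escalated to 120 mg/day", and Section 6.1.2.5 adds: "The 3 remaining participants who initiated tolebrutinib 60 mg will remain at 60 mg and not be escalated to 120 mg/day". At most four participants can contribute to either endpoint.

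**The concern.** Two tests of one objective, each at 0.025, have the form of a single-step Bonferroni split of 0.05. For two tests there is a well-known sharper rule with the same overall bound. Holm compares the smaller p-value with 0.025 and, only if that is met, the other with 0.05.

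Under the fixed rule, a pair such as p = 0.01 and p = 0.04 is reported as one significant and one non-significant endpoint. Under Holm both are significant. A fall in T1 together with a fall in size would be the most persuasive evidence of repair, and with at most four participants a p-value between 0.025 and 0.05 on one endpoint is quite possible. The sample cannot grow, so the decision rule is one of the few design features that can still be changed.

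**Working it through.** **1. The plan's own figure.** The two thresholds are 0.025 and 0.025 (Section 9.4.3, repeated in Section 3). Their sum, 0.025 + 0.025 = 0.05, bounds the error over the pair under any dependence. With independent tests and both nulls true, it is 1 − 0.975² = 0.0494. The plan gives no power, effect size or SD for either endpoint, so there is no power figure to reproduce.

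**2. Holm never rejects less.** If the smaller p-value exceeds 0.025, neither rule rejects anything. If it does not, both rules reject that endpoint; the other is then rejected at 0.025 under the fixed rule and at 0.05 under Holm. The rules differ only when one p-value is at or below 0.025 and the other lies between 0.025 and 0.05.

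**3. The bound is the same.** If both nulls are true, an error requires the smaller p-value to be at or below 0.025, with probability at most 0.025 + 0.025 = 0.05. If one null is true, it can be rejected only when its own p-value is at or below 0.05. Steps 2 and 3 need only valid p-values, not a particular model.

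**4. Illustrative size.** Assumptions: one rim-minus-non-rim change per participant, n = 4, two-sided one-sample t test with 3 df, and equal standardised effects (mean divided by SD across participants) on both endpoints. There were 200,000 simulated trials per setting. The critical |t| is 4.18 at 0.025 and 3.18 at 0.05. Each cell shows fixed rule → Holm, in percent.

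| Effect | Correlation | Power per endpoint | Power for both | At least one (either rule) |
|---|---|---|---|---|
| 0.5 | 0 | 5.8 → 6.1 | 0.3 → 1.0 | 11.3 |
| 0.5 | 0.5 | 5.9 → 6.5 | 0.8 → 2.1 | 10.9 |
| 1.0 | 0 | 16.7 → 18.7 | 2.8 → 6.8 | 30.6 |
| 1.0 | 0.5 | 16.8 → 19.6 | 4.8 → 10.4 | 28.7 |
| 1.5 | 0 | 34.6 → 41.2 | 12.1 → 25.1 | 57.2 |
| 1.5 | 0.5 | 34.5 → 41.6 | 15.9 → 30.0 | 53.1 |
| 2.0 | 0 | 55.3 → 66.5 | 30.6 → 52.9 | 80.1 |
| 2.0 | 0.5 | 55.3 → 65.8 | 35.5 → 56.5 | 75.1 |

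Check at effect 2.0, correlation 0: at least one = sum of the two endpoint powers − both. Fixed rule: 0.5527 + 0.5535 − 0.3056 = 0.8006. Holm: 0.6644 + 0.6650 − 0.5288 = 0.8006. The two agree, as step 2 requires.

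The gain in power for both is also the share of trials in which the decision changes: about 1% at effect 0.5, 4 to 6% at 1.0, and 21 to 22% at 2.0.

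**5. Error rates.** With both nulls true, the chance of any rejection is 4.9% (correlation 0) or 4.8% (correlation 0.5) under either rule. With one null true and the other effect 2.0, the error on the null endpoint goes from 2.5% to 3.9% (correlation 0) or 4.1% (correlation 0.5). The first figure follows by hand: under independence the error is 0.025 + 0.025 × (power of the other endpoint at 0.025) = 0.025 + 0.025 × 0.55 = 0.039.

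**The case against.** The strongest reply is that nothing here is wrong. A fixed 0.025 is a legitimate choice, and Holm in its place is a matter of efficiency. That stands.

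A reader might infer that the stricter second threshold buys nothing in error control. The documents and the arithmetic do not support that. When only one effect is real, the fixed rule holds the other endpoint at 2.5%, and Holm lets it rise to about 4%. Both respect the 5% bound, but the fixed rule is tighter in that case.

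A reader might also infer that the plan loses power generally. It does not: the chance of a first significant endpoint is the same under both rules. The gain lies in the second endpoint, and Section 9.1 gives each endpoint its own hypothesis without making success on both a criterion.

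The large gains need large effects, and the documents supply no effect size or SD. The t test stands in for an analysis that the plan leaves open, so the power figures may not carry over to lesion-level models. The dominance of Holm does carry over.

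Sidedness matters too. The hypotheses are directional. If 0.025 was meant as a one-sided level per test, the 0.05 bound on the pair still holds, but Holm's second step would be one-sided 0.05, equivalent to two-sided 0.10. Any new wording must settle this.

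Last, the change would come late. The study is open-label, with only the MRI analysts blinded, and only to time point (6.3). All escalated participants have been treated, and the DSMB sees efficacy data twice a year (10.6). Relaxing a threshold at this stage has some cost in credibility. That is a reason to date and document the change, and it makes the change optional rather than necessary.

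**Conclusion.** This is a cheap improvement, not an error. The fixed 0.025 for each endpoint validly bounds the pair at 0.05. Holm has the same bound under any correlation and never rejects less; that conclusion is free of modelling assumptions.

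The size of the gain is illustrative. It is negligible at a standardised effect of 0.5, 2 to 3 points per endpoint at 1.0, and about 11 points per endpoint at 2.0, where power for both rises by 21 to 22 points. These figures rest on four completers, one contrast per participant, two-sided t tests and correlation 0 to 0.5. The 5% family is inferred from 0.025 + 0.025, because the plan does not name one.

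It would go too far to conclude that Holm makes these endpoints adequately powered. At an effect of 1.0, power per endpoint stays below 20% under either rule. The binding limit is four participants, and no multiplicity rule changes that. Nor does either rule cover the primary test, which keeps its separate 0.05.

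**What to change.** In Sections 3 and 9.4.3, replace the two threshold sentences with: *The T1 and size tests (two-sided) form one family at 0.05; the smaller p-value is compared with 0.025 and, if significant, the other with 0.05 (Holm).* This also names the family and states sidedness, which the plan now leaves open. If the authors meant 0.025 as a one-sided level, they should say so and set the family level to match before adopting the wording.

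Section 9 says there is no separate SAP, so the protocol is the place for the change. Under the Statement of Compliance an amendment needs IRB approval before it is implemented. It should be approved and dated before the week-144 data (48 weeks at 60 mg plus 96 weeks at 120 mg) are analysed, with a note that the outcome results were not used in making it.

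The costs are one amended sentence per section, the late timing, and the higher error on a null endpoint when the other effect is real (2.5% to about 4%). The plan calls for no confidence intervals on these endpoints; if any are reported, they will not always mirror the step-down decision on the second endpoint.

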# **1.2 SCHEMA**

**Control:** 

## Initial Cohort (tolebrutinib 60 mg)

## Cohort A (tolebrutinib 60 mg $\rightarrow$ 120 mg)#:

			8	t	Treatmolebrutinib	ent:											atment: nib 120 mg							erm Extensi utinib 120n	
Treatment: anti-CD20 for >6 months of most recent dose	Day 0 • First • Dose	24–48 hours • Phone call	Week 2 (±7 days) • Blood work	Week 4 (±7 days) Blood work	Week 6 (±7 days) •Blood work	Week 8 (±7 days) • Bload • wark	Week 10 (±7 days) • Bload • work	Week 12 (±7 days) - History - Exam - Bisodwark - ECG - LP	Week 24 (±14 days) - History - Exam - Scales - 77 MRI - Bioodwork - ECG	Week 36) (±14 days • History • Exam • Brain: MRI • Bloodwork • ECG	Week 48 (±14 doys) - History - Scalics - 77 MRI - Biodwork - ECG - LP	Week 48 + 24-48 hours • Phone call	Week 52 (±7 days) • Bloodwork	Week 56 (±7 days) • Woodwork	Week 60 (±14 days) • History • Exam • Brain MRI • Bloodwork • ECG	Week 72 (±14 days) - Hiatory - Scans - Scales - 77 MRI - Bloodwork - ECG	(±14 days) • History • Exam	(±14 days)	Week 108 (±14 days) • Kistory • Scales • Brain MRI • Bloodwork • ECG	Week 120 (±14 days) • History • Exam • Scales • 77 MRI • Bloodwork • ECG	Week 132 (±14 days) • History • Exam • Scales • Brain MRI • Bioodwork • ECG	Week 144 (±14 days) - History - Exam - Scales - 7T MRI - Biloadwork - ECG	Week 168 (±28 days) • History • Exam • Scales • 77 MRI • Bloodwork • ECG	Week 192 (±28 days) Exam Scales 77 MRI Bibodwork ECG	
			•							Prin	nary Out	come													

# See section 6.1.2.5. Participants (n=4) in cohort A, who had initiated tolebrutinib 60mg and previously escalated to 120 mg/ day will remain at that dose and the 3 remaining participants, in the initial cohort, who initiated tolebrutinib 60mg and not be escalated to 120mg/day.

# **1.3** SCHEDULE OF ACTIVITIES (SOA)

Initial cohort (participants who choose not to escalate dose from tolebrutinib 60 mg):

Procedures	Baseline (≤14 days prior	Day 0	24 – 48 Hours Follow-Up	Week 2 (±7 days)	Week 4 (±7 days)	Week 6 (±7 days)	Week 8 (±7 days)	Week 10 (±7 days)	Week 12 (±7 days)	Week 24 (±14 days)	Week 36 (±14 days)	Week 48 (±14 days)	Week 60 (±14 days)	Week 72 (±14 days)	Week 84 (±14 days)	Week 96 (±14 days)	Every 24 weeks (±28 days)*
Informed consent	Х																
Medical history	Х																
Interval history/neurological exam	Х								Х	Х	Х	Х	Х	Х	Х	Х	Х
Vital signs	Х	Х							Х	Х	Х	Х	Х	Х	Х	Х	Х
Clinical measures	Х									Х		Х		Х		Х	Х
(EDSS, 9HPT, 25FTW, SNRS, SDMT)																	
Clinical labs	Х			X 	X 	X 	X 	X 	X 	Х	X 	Х	X 	Х	X 	Х	Х
Research labs	Х								Х	Х	Х	Х	Х	Х	Х	Х	Х
Pregnancy test (if applicable)	Х	Х							Х	Х	Х	Х	Х	Х	Х	Х	Х
Brain MRI (7-tesla)	Х									Х		Х		Х		Х	Х
Brain MRI									Х		Х		Х		Х		
ECG	Х								Х	Х	Х	Х	Х	Х	Х	Х	Х
Lumbar puncture	Х								Х			Х					
Tolebrutinib first dose		Х															
Follow-up phone call			Х														
Tolebrutinib study drug dispensed		Х							Х	Х	Х	Х	Х	Х	Х	Х	Х

\*Long term extension until tolebrutinib is marketed or until its development is halted.

Safety labs.

Liver-specific safety labs (AST, ALT, alkaline phosphatase, total bilirubin)

#### Abbreviated Title: BRaKe-MS Version Date: 6/21/2023

Cohort A (tolebrutinib 60 mg  $\rightarrow$  120 mg)#:

Procedures	Baseline (≤14 days	Day 0	24 – 48 Hours Follow-Up	Week 2 (±7 days)	Week 4 (±7 days)	Week 6 (±7 days)	Week 8 (±7 days)	Week 10 (±7 days)	Week 12 (±7 days)	Week 24 (±14 days)	Week 36 (±14 days)	Week 48 (±14 days)	Week 48+24-48 hours	Week 52 (±7 days)	Week 56 (±7 days)	Week 60 (±14 days)	Week 72 (±14 days)	Week 84 (±14 days)	Week 96 (±14 days)	Week 108 (±14 days)	Week 120 (±14 days)	Week 132 (±14	Week 144 (±14	Every 24 weeks (±28
Informed consent	Х												_											
Medical history	Х																							
Interval history/neurological	Х								Х	Х	Х	Х				Х	Х	Х	Х	Х	Х	Х	Х	Х
exam																								
Vital signs	Х	Х							Х	Х	Х	Х				Х	Х	Х	Х	Х	Х	Х	Х	Х
Clinical measures	Х									Х		Х					Х		Х	Х	Х	Х	Х	Х
(EDSS, 9HPT, 25FTW, SNRS,																								
SDMT)																								
Clinical labs	Х			X 	X1	X 	X1	X 	X1	Х	X1	Х		X1	X 	X1	Х	X1	Х	X1	Х	X1	Х	Х
Research labs	Х								Х	Х	Х	Х				Х	Х	Х	Х	Х	Х	Х	Х	Х
Pregnancy test (if applicable)	Х	Х							Х	Х	Х	Х				Х	Х	Х	Х	Х	Х	Х	Х	Х
Brain MRI (7-tesla)	Х									Х		Х					Х		Х		Х		Х	Х
Brain MRI									Х		Х					Х		Х		Х		Х		
ECG	Х								Х	Х	Х	Х				Х	Х	Х	Х	Х	Х	Х	Х	Х
Lumbar puncture	Х								Х			Х							Х					
Tolebrutinib first dose at each		Х										Х												
dose level																								
Follow-up phone call			Х										Х											
Tolebrutinib study drug dispensed		Х							Х	Х	Х	Х				Х	Х	Х	Х	Х	Х	Х	Х	Х

\*Long term extension until tolebrutinib is marketed or until its development is halted.

# See section 6.1.2.5. Participants (n=4) in cohort A, who had initiated tolebrutinib 60mg and previously escalated to 120 mg/ day will remain at that dose and the 3 remaining participants in the initial cohort, who initiated tolebrutinib 60mg will remain at 60mg and not be escalated to 120mg/day.

Safety labs.

Liver-specific safety labs (AST, ALT, alkaline phosphatase, total bilirubin)

11

